Patients at high risk of emergency hospital admission (top quintile) or with long-term conditions are offered enrolment in the programme during the course of a consultation with their General Practitioner (GP). Enrolment on the programme is considered complete if patients consent to be enrolled on the programme and consent for their data to be shared with the WELC Integrated Care Programme partners, and this consent is recorded on the electronic patient record by the GP. Enrolment started in April 2012, with a total of 29 patients enrolling in the first 12 months. The following fiscal year (2013-2014) saw another 906 patients enrol on to the programme. Numbers are increasing rapidly, with currently 11,940 patients on the pathway (1.3% of all patients, in comparison to the 20% targeted) (source: WELC Data Cube).

The integrated care programme is trying to achieve its goals through a combination of patient engagement; joint decision making and accountability; clinical leadership and culture development; information sharing and decision support; and aligned incentives and reimbursement models. Although patients are either enrolled or not enrolled on the programme, the actual intervention may differ from patient to patient and across different CCGs. The Integrated Care Programme comprises nine categories of interventions:

1. Self-care, behaviour and expectation management;
2. Care planning;
3. Health and social care navigation;
4. Case management;
5. Specialist input in the community;
6. Discharge support for mental health patients from secondary to primary care;
7. Rapid response with short term re-ablement;
8. Mental health liaison; and
9. Discharge support from the acute community.

The exact interventions can be specific to local arrangements, and so are difficult to generalise across a larger population. Therefore, the evaluation proposed in this protocol aims to evaluate the overall effect of enrolment onto the integrated care pathway, rather than looking at effect of the individual

interventions offered during this pathway. We will, however, try to describe the occurrence of particular interventions.

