A small number of patients provided consent to be on the pathway or for their data to be shared but not both. Because there is some ambiguity about the care received by these patients, they will be excluded from the study.

The initial findings of the evaluation will be based on outcomes over the six months following enrolment. This relatively short follow-up period will allow for timely results by the end of 2015. Further analysis will be based on a follow-up period of twelve months following enrolment; however patient-level data required for this analysis are not expected to be available before February 2015 (see ‘Timescale’ below for more details).

Intervention

The focus of this study is to evaluate the overall integrated care pathway, and thus we will assess patient outcomes from the date of enrolment onto this pathway. After the enrolment on the programme a patient will receive specific interventions at varying intervals that greatly influence the effect of the overall ‘treatment’ (see figure below).

We will report the overall duration of time spent on the integrated care pathway using Kaplan-Meier curves (Kaplan & Meier 1958). These show the proportion of patients remaining on the pathway after various numbers of days spent on the pathway. In some cases, the lag between enrolment on the pathway and receiving first ‘different-from-normal’ care might be substantial, and so we will explore whether the individual interventions illustrated in the figure below can be identified from the line-level data.

Endpoints

The Integrated Care Program has identified a wide range of Key Performance Indicators (KPIs). These indicators span: quantitative metrics to assess how care is being integrated; metrics on reviews of individual patient cases and care plans; and metrics of health care utilisation. This last category of indicators is most relevant to this study and includes:

- Number of GP appointments (*e.g.*, per head, per 12 months);
- Number of urgent referrals;
- Number of hospital bed days per patient;
- Number of weekend discharges from hospital;
- Secondary care cost (PbR);
- Number of emergency hospital admissions;
- Number of avoidable hospital admissions;
- Number of A&E attendances; and
- 30-day hospital readmission rates.

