Our primary endpoint is the number of emergency hospital admissions per patient, which is a commonly used endpoint in evaluative studies of integrated care. Our secondary endpoint is the number of hospital bed days per patient over twelve months, as this reflects changes to the length of stay in hospital as well as the number of admissions.

Other endpoints will be the notional cost of care per patient, including primary and secondary care cost and other indicators listed above.

Sample size calculation

Our sample size will be sufficient to identify a 15% change in emergency admissions between the enrolled patients and the matched control group. Our sample size calculation was performed in SAS with 90% power and a two-sided p-value of 0.05. We assumed an average number of emergency admissions per patient per year of 0.6 with a standard deviation of 1.4. These assumptions are based on a previous study with a similar population base (Steventon, Bardsley, Billings, Dixon, et al. 2012).

The sample size calculation indicate that in order to identify a 15% change in emergency admission a sample size of 10,174 is required in case of a balanced sample (1 control per enrolled patient), or 11,445 in case of a sample with two controls per enrolled patient. In comparison, we estimate that our study will include at least 6,360 integrated care patients. In a matched control design with one control patient per integrated care patient, the total sample size would therefore be 12,720 patients. If there were two control patients per integrated care patient, the total sample size would be higher, at 19,080.

Control group

In the absence of a randomised controlled trial, we will compare the outcomes of the integrated care cohort with a retrospectively matched control group. In other words, line-level routine, patient information will be used to characterise the integrated care patients as well as possible, and then select, for every patient, matched controls that were not enrolled onto the programme but had similar observed characteristics to the enrolled patient. These matched patients will form the control group for the evaluation of the programme.

Control patients will be registered with a general practice in the WELC area, and will not have been enrolled onto the integrated care pathway at any point before the end of our follow-up period.

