Preliminary analysis of aggregated data from the WELC Integrated Care Programme (using the Data Cube) suggests that the pool of potential matches is sufficiently large to select matched controls within cluster (*i.e.*, geographically clustered GPs) and within the same risk-band (top 0.5%, 0.5-5%, or 5-20%). This is because enrolment rates at cluster level vary between 17% and 38%, and enrolment rates for the different risk-bands are 50%, 24% and 2%, respectively.

Matching will be done to optimise the similarity of integrated care and matched control groups with respect to variables that are likely to be predictive of the endpoints. These variables will include:

predictive risk score; age; gender; ethnicity; prior primary and secondary care utilisation; a measure of socioeconomic deprivation (the Index of Multiple Deprivation, attributed to the Lower Super Output Area of residence); existing diagnoses of health care conditions; and numbers of prescription medications. Many of these variables feature in the Combined Predictive Model (Wennberg et al. 2006), but are included in our matching algorithm so that the groups will be similar in terms of these more detailed variables as well as the overall risk score.

To increase the number of potential controls available for the analysis, we will assign each potential control up to 12 index dates, one for each month from January 2014 to December 2014, assuming that the patient is alive at each of these time points. Baseline variables (*e.g.*, age and prior primary and secondary care utilisation) will then be calculated at each of these index dates, and each control patient will provide the matching algorithm with up to twelve observations.

Matched control observations will be selected using the genetic matching algorithm, which is a computer-intensive search procedure that produces more closely balanced groups than traditional approaches such as nearest neighbour matching on the propensity score (Sekhon & Grieve 2012). Balance will be assessed using the standardised difference, which is defined as the difference in means as a proportion of the pooled standard deviation (Austin 2009). Although the standardised difference would ideally be minimised without limit, a threshold of 10% has been used to describe meaningful difference (Normand et al. 2001). We will adjust the parameters in the genetic matching algorithm until we obtain standardised differences below these thresholds.

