The matching will be conducted with replacement, meaning that a patient might be used as the control for multiple integrated care patients. Our preference is to select two control observations per patient, as this would increase the precision of our estimates of the effect of the integrated care pathway on patient outcomes (*i.e.*, reduce the width of our confidence intervals, meaning we can be more sure about the effect size). However, if it is not possible to obtain adequate balance when selecting two controls per patient, we will rerun the matching algorithm when selecting one control per patient.

Statistical method

After adequate balance has been obtained, we will estimate the effect of the integrated care pathway on patient outcomes by fitting regression models to the data. These models will adjust for residual differences remaining between the groups in the baseline variables after matching. We will include all patients in these analyses, even if they died or moved away from the WELC area during the 12-month follow-up period.

For our primary endpoint, number of emergency hospital admissions, use of Poisson regression seems appropriate, but depending on the empirical distribution of this endpoint, alternative distributions will be considered (*e.g.*, negative binomial). We assume that ordinary least squares (linear) regression will be used

for our secondary endpoint, the number of hospital bed days. On receipt of the line-level data, we will test the suitability of these assumptions, and consider alternative distributions if appropriate. We will follow a similar procedure for other endpoints making sure that assumptions on distributions are appropriate.

Subgroup analysis

The main analysis will be pooled across all three CCGs and across all risk bands, as this approach is necessary to ensure adequate sample size. However, we will also examine whether there is evidence that the integrated care pathway affected the outcomes of certain subgroups of patients more or less than average. Specifically, we will examine subgroups defined by CCG (Newham, Tower Hamlets, and Waltham Forest) and risk band (top 0.5%, 0.5-5%, and 5-20%). We will also distinguish between patients with and without a recorded mental health condition.

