mortality within a 12-month period, then differences in mortality rates would make us doubt the performance of the matching. For example, if enrolled patients died at a higher rate than matched control patients, this might suggest that they were in worse health than controls at the point of enrolment (Steventon, Bardsley, Billings, Georghiou, et al. 2012).

A second strategy is to test the robustness of the study findings to hypothetical unobserved confounders that we will simulate (Carnegie et al. 2013). The crucial dimensions are the strength of association between the confounder and treatment assignment, and likewise the strength of the association between the confounder with outcome (for example, if the hypothetical confounder is social isolation, then the degree to which socially isolated individuals are disproportionately enrolled onto the integrated care pathway and the extent to which they have worse outcomes than other patients who are not as socially isolated). We will make various assumptions about these associations and assess how strong they must be to overturn our initial evaluation findings. We will then compare these associations with those observed for known variables (*e.g.*, age) to assess how likely they are to have occurred.

GOVERNANCE

Since WELC has already established an evaluation steering group for the programme, we propose that the scope of this group is expanded to include consideration of this additional work. Formal ethical review is not required for the analyses outlined in the current document, as they constitute a service evaluation and retrospective secondary use of pseudonymised data.

TIMESCALE

The following table shows the anticipated timeframe for the completion of these analyses. This assumes timely approval of the protocol by the evaluation steering group and timely transfer of the line-level data.

Milestone	Date
Approval of protocol by the evaluation steering group	June 2015
Permission to access Tower Hamlets data	July 2015
Data transferred	April 2016
Permission to access Newham data, and subsequent additional data transfer	May 2016 (if successful in obtaining permissions)
Preliminary analysis complete	end of October 2016
Present findings to stakeholders	October 2016
Final analysis complete. Report released to the sites	December 2016
Related journal articles submitted for peer-review	March 2016

DISSEMINATION

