We will require all data sets to be pseudonymised before transfer; no patient identifiable information (*e.g.*, name, address, full date of birth) are required to complete the analysis. Pseudonymising NHS number (*i.e.*, apply a one-way hash algorithm to the NHS number, only known to the data controller) allows the data to be updated and extended, if necessary. The data sets will need to include line-level data for the top twenty per cent of patients at risk of emergency hospital admission aged over fifty years in the WELC area¹, spanning the period 1 January 2011 to 31 December 2015. Both age and risk-score vary over time, so the exact definition of these extracts will be defined in the detailed specification. We will need Read-coded GP data on registrations with GPs, prescriptions, diagnoses, and encounters, together with line-level data from the admitted patient care, outpatient and accident and emergency commissioning data sets. It would greatly assist us if some derived variables were available for the analysis (for example, the Combined Model score and constituent variables) – this would also help us standardise our variable definitions with those used locally.

¹ Note that only data from Tower Hamlets CCG and Newham CCG is to be included.

References

- Austin, P.C., 2009. Balance diagnostics for comparing the distribution of baseline covariates between treatment groups in propensity-score matched samples. *Statistics in Medicine*, 28, pp.3083–3107.
- Kaplan, E.L. & Meier, P., 1958. Nonparametric estimation from incomplete observations. *Journal of the American Statistical Association*, 53(282), pp.457–481.
- Normand, S.-L.T. et al., 2001. Validating recommendations for coronary angiography following acute myocardial infarction in the elderly: a matched analysis using propensity scores. *Journal of Clinical Epidemiology*, 54(4), pp.387–398. Available at: <http://www.ncbi.nlm.nih.gov/pubmed/11297888>.
- Roland, M. et al., 2005. Follow up of people aged 65 and over with a history of emergency admissions: analysis of routine admission data. *BMJ*, 330, pp.289–292. Available at: <http://www.bmj.com/content/330/7486/289.short> [Accessed August 21, 2012].

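### Controls must stay un-enrolled until the end of follow-up, so they are selected on events after the index date; this distorts the mortality check and may lower control admissions

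*Protocol*

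**What the plan says.** All places are in the Protocol.

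- **Control group:** a control "will not have been enrolled onto the integrated care pathway at any point before the end of our follow-up period". Each potential control receives up to twelve index dates, "one for each month from January 2014 to December 2014, assuming that the patient is alive at each of these time points". Being alive is the only condition stated at the index date itself.
- **Study cohort:** "Further analysis will be based on a follow-up period of twelve months following enrolment". Initial findings use six months.
- **Statistical method:** "We will include all patients in these analyses, even if they died or moved away from the WELC area during the 12-month follow-up period". Nothing is said about controls who enrol later, because the eligibility rule has already removed them.
- **Control group, on uptake:** for the top 0.5%, 0.5-5% and 5-20% of risk, "enrolment rates for the different risk-bands are 50%, 24% and 2%, respectively".
- **Introduction:** GPs offer enrolment in a consultation, to patients in the top fifth of admission risk or with long-term conditions.
- **Sensitivity analysis for unobserved confounding:** mortality is compared between the groups, and "differences in mortality rates would make us doubt the performance of the matching".
- **Data specification:** the extract is "spanning the period 1 January 2011 to 31 December 2015".

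**The concern.** Whether a person may serve as a control at a given index month depends on the following year, or on up to two years for a January 2014 index date if the end of follow-up means the end of the data. The enrolled group is not filtered in this way.

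Two consequences follow.

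1. **Mortality.** Enrolment requires being alive. Deaths stay in the control group while some survivors leave it, so its death rate tends to rise for a reason unrelated to the quality of the matching. The check could then miss enrolled patients who were truly sicker, or raise a false alarm.
2. **Emergency admissions (primary endpoint).** If patients who are admitted after the index date become more likely to be offered enrolment, the controls who remain are those with fewer admissions. A real benefit would be partly hidden, or an ineffective programme would look harmful.

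No other part of the plan deals with this. Matching and regression use baseline variables. The person-years analysis covers leaving the programme, death and moving away. The simulated-confounder analysis concerns unmeasured factors associated with treatment assignment and outcome, not selection on later events.

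**Working it through.** **The plan's own figure.** With a mean of 0.6, SD 1.4, difference 0.15 × 0.6 = 0.09, two-sided 0.05 and 90% power, the two-means formula gives 5,086 per group, or 10,172 in total at 1:1, and 3,814 + 7,628 = 11,442 at 1:2. The Protocol states 10,174 and 11,445. The sample size is reproduced and is not in question. It supplies the yardstick of 15%.

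**How many people could be affected.** Patients enrolled during 2014 (at least 6,360) cannot be controls at earlier 2014 index dates in the twelve-month analysis. Beyond them, current enrolment of 11,940 less 6,360 less 935 (29 + 906) leaves 4,645. This is an upper bound on relevant later enrolees from that subtraction: the 11,940 is undated and programme-wide, about 85% of enrolees fall in the study's age and risk group, and a footnote limits the data to two CCGs.

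**Mortality, closed form.** Let annual mortality be m and 12-month enrolment be e, independent of each other (both assumed). Put h = −ln(1−m) and k = −ln(1−e).

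- Death before enrolment: D = h/(h+k) × (1 − exp(−(h+k))).
- Alive and un-enrolled at 12 months: S = exp(−(h+k)).
- Mortality among the never-enrolled: D/(D+S).

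For m = 10% and e = 24%: h = 0.1054, k = 0.2744, S = 0.90 × 0.76 = 0.684, D = 0.1054/0.3798 × 0.316 = 0.0877. The result is 0.0877/0.7717 = 11.4% instead of 10%. At e = 2%, 10% and 50% it is 10.1%, 10.5% and 13.9%. If the look-ahead is 24 months, e = 24% gives 0.0877/(0.0877 + 0.684 × 0.7717) = 14.2%.

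For m = 9% and enrolment of 1% or 2% per month (k = −12 ln 0.99 or −12 ln 0.98), the same formula gives 9.5% and 10.1%, about 6% and 12% too high in relative terms.

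**Admissions, simulation with no programme effect.** Admissions are gamma-Poisson with the plan's mean 0.6 and SD 1.4 (gamma shape 0.36/(1.96 − 0.6) = 0.265). Assumed, not in the Protocol: enrolment of 1-2% per month, a hazard 2-3 times higher after an admission, and 9% annual mortality. Never-enrolled controls are compared with all controls eligible at the index date.

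| Quantity in never-enrolled controls | Result |
|---|---|
| Admissions, no baseline adjustment | about 5-20% too low |
| Admissions, standardised to prior-year admissions | about 3-13% too low |
| Admissions, enrolment unrelated to admissions | about 1% too low or less |
| Mortality, across scenarios | about 5-14% too high |

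At 9% mortality the last row is 9 × 0.05 = 0.45 to 9 × 0.14 = 1.26 percentage points. The standard error of the mortality difference with 6,360 per group is √(2 × 0.09 × 0.91/6,360) = 0.51 points, so the distortion is about 1 to 2.5 standard errors (ignoring re-use of controls).

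**The case against.** **Matching absorbs part of the problem.** Controls are matched within risk band and on risk score, prior utilisation, diagnoses and prescriptions. Much of the unadjusted gap is stable between-patient frailty, which these variables partly capture. This stands: the 5-20% figure should not be set against the 15% target, and matching on more than prior-year admissions could shrink the 3-13% further. It cannot remove the part that arises from events after the index date.

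**The driving parameter is not in the document.** The uptake rates of 50%, 24% and 2% are cumulative levels by risk band, and band is itself a matching factor. They do not show that a new admission raises the chance of enrolment. This also stands. A reader might infer that the primary estimate is certainly biased against the programme; the Protocol makes that direction plausible through the enrolment route but does not establish it.

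**The mortality sign is not guaranteed.** Removing controls who enrol because they are deteriorating pushes control mortality down. The upward push prevailed in the scenarios examined, but that is not proof.

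**The rule has a purpose.** It keeps the control group free of the intervention. Keeping later enrolees as controls without censoring would dilute the effect: at 24% later enrolment, (1 − 0.76)/0.2744 = 0.875 of control time is un-enrolled, so 15% becomes 13.1% and power at 1:1 with 6,360 enrolled falls from 0.952 to 0.887. This argues for censoring with weights, not for selecting on the future.

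**Two further inferences go too far.** That every later enrolee is lost as a control is not supported: under a twelve-month look-ahead, someone enrolling in 2015 remains usable at early-2014 index dates. That the control pool must differ between the six- and twelve-month analyses depends on whether the end of follow-up is a personal or a calendar date, which the wording leaves open.

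**Conclusion.** The point holds as a cheap improvement. The selection on later enrolment, applied to controls only, follows directly from the Protocol's wording and is not corrected anywhere in it. Its most dependable effect is on the mortality check: control mortality is probably overstated by about 5-14% in relative terms under the stated enrolment and mortality assumptions, with the sign likely but unproven.

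The effect on emergency admissions is conditional. It is an illustrative 3-13% deficit if a post-index admission doubles or triples the chance of enrolment, and about 1% or less if it does not. The bias is small where enrolment during follow-up is low, as is likely in the 5-20% risk band, and larger where uptake is high. The document does not support reading this as proof that the study's main result will be wrong.

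**What to change.** 1. **Eligibility.** Replace the never-enrolled condition with: at each index month, controls are patients who are registered, eligible and not enrolled at that date, whatever happens later.
2. **Main analysis.** Censor each control at its own later enrolment. Use a person-time offset and inverse-probability-of-censoring weights that include time-updated admissions. The weights are needed: in an illustrative simulation, censoring alone left about 1-5% bias in admissions. The enrolled patient's follow-up need not be cut short, so the method works with one or two controls per patient.
3. **Standard errors.** Cluster by patient or use the bootstrap, because a later enrolee can appear first as a control and then as an enrolled patient, and matching is with replacement.
4. **Mortality check.** Run it on these controls with the same weights.
5. **Sensitivity analysis.** Keep the never-enrolled control group here, and state whether its end of follow-up is counted from each index date or is a calendar date.

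**Cost:** protocol wording and extra programming, somewhat less control follow-up, and added variance from the weights. No new data are needed: applying the present rule already requires enrolment dates, and an extract running to the end of 2015 covers twelve months after the last 2014 index date.

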We propose to evaluate the integrated care programme using a (matched) control group, rather than solely tracking metrics using the data cube for intervention patients. Looking at patient level data, and matching patients enrolled in the programme with similar patients who were not enrolled, allows us to compare the outcome measures of enrolled patients with a counterfactual. This is particularly important given the tendency of patients with a history of hospital admissions to see reductions in admissions over time even in the absence of a specific intervention ('regression to the mean') (Roland et al. 2005).

The first step of the evaluation would be to assess the feasibility of the matched control approach. There are risks that we might not find controls that are adequately matched to enrolled patients on observed baseline variables, or that there might be unobserved confounding (*e.g.*, as indicated by differential mortality rates between enrolled patients and the control group). Provided adequate controls can be found, we propose to evaluate the programme as described below.

METHODS

Study cohort

We will study patients enrolled onto the integrated care pathway in 2014 (*i.e.*, between 1 January 2014 and 31 December 2014) who were in the top 20% in terms of their risk of emergency hospital admission and who were aged fifty years or over. The cohort will include patients from all three CCGs, though we will also analyse the patients in the three CCGs separately.

This cohort has been chosen to ensure a sufficiently large study cohort of at least 6,360 patients (*i.e.*, the difference between the total number of patients enrolled on 1 January 2015 and 1 January 2014, source: WELC Data Cube). The total number of patients in the cohort is expected to be higher than this, as enrolled patients who died, or moved out of the three CCGs are not included in this total.

This cohort includes 85 per cent of patients currently enrolled in the programme. By limiting the study to this cohort ensures that sufficient information is used to evaluate the effect of the programme for different age groups robustly. Evaluation of the programme for younger patients, or patients that are less at risk of emergency hospital admission would add too much uncertainty to the study's findings at this stage. Limiting the cohort also allows for the matching to be completed in a timely manner, as matching algorithms used are very time consuming.

[figure not shown]

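### The enrolment rates given as proof of a sufficient control pool have no stated denominator and do not support sufficiency in the top 0.5% risk band, where the group-level balance rule may miss poor matching

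*Protocol*

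**What the plan says.** Under Methods, Control group, the protocol reports that preliminary aggregate data "suggests that the pool of potential matches is sufficiently large to select matched controls within cluster" and within one of three risk bands: the top 0.5%, 0.5-5% and 5-20%. The reason given is that "enrolment rates at cluster level vary between 17% and 38%, and enrolment rates for the different risk-bands are 50%, 24% and 2%, respectively". No denominator, age restriction or date is attached to either set of rates.

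Other parts of the protocol bear on this:

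- Control group: each potential control may contribute up to 12 monthly observations, and matching is with replacement. "Our preference is to select two control observations per patient", with one as the fallback if balance is inadequate. The 10% standardised-difference threshold is described for the integrated care and matched control groups.
- Control group: controls must be on the list of a WELC practice. A second condition is that they "will not have been enrolled onto the integrated care pathway at any point before the end of our follow-up period".
- Study cohort: the cohort is 2014 enrolees aged 50 or over in the top 20% of risk, at least 6,360 patients. "This cohort includes 85 per cent of patients currently enrolled in the programme".
- Introduction: there are "currently 11,940 patients on the pathway (1.3% of all patients, in comparison to the 20% targeted").
- Subgroup analysis: effects are to be examined by risk band, including the top 0.5%.
- Data specification, footnote: only Tower Hamlets and Newham data are to be included.

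**The concern.** The sufficiency statement rests on these rates alone, and they do not carry it, for three reasons.

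- The two sets of rates do not fit together if both describe the top 20%, which is the study's risk range.
- Both are marginal. A rate for each cluster and a rate for each band say nothing direct about the cluster-by-band cells in which controls would be sought.
- For the top 0.5% band the quoted 50% points away from an ample pool.

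Where the pool is thin, the algorithm has little choice among the people left un-enrolled. The protocol's own section on unobserved confounding accepts that professionals may have selected patients and that patients differ in willingness to consent. Such selection matters most where uptake is highest. If balance is judged only on the two groups as a whole, good matches in the larger bands could hide poor ones in the top band. The top-band subgroup estimate would then be biased, and some of that bias would pass into the pooled estimate.

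**Working it through.** **Inputs.** Band widths, from the band limits in Control group: 0.5, 4.5 and 15 percentage points of the population. Band enrolment rates: 50%, 24% and 2%. Cluster rates: 17% to 38%. Overall enrolment, from the Introduction: 11,940, or 1.3%.

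**1. The plan's overall figure.** 11,940 / 0.013 ≈ 918,000 patients, which fits the Introduction's population of almost one million.

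**2. Average implied by the band rates.**

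- Enrolled share of the population: 0.5 × 50% + 4.5 × 24% + 15 × 2% = 0.25 + 1.08 + 0.30 = 1.63 points.
- Over the top 20%: 1.63 / 20 = 8.15%. If every band rate is off by half a point in the same direction, the range is 7.65% to 8.65%.
- Over the top 5%: (0.25 + 1.08) / 5 = 26.6%.

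An average of 8.15% is impossible if every cluster lies between 17% and 38% on the same denominator. An average of 26.6% is possible.

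**3. Could the age limit reconcile them?** Let W be the share of the eligible group that lies in the top 5%, with the mix inside the top 5% unchanged (assumption). Then 0.266W + 0.02(1 − W) ≥ 0.17 gives W ≥ 0.15 / 0.246 = 61%. By band width alone W is 5 / 20 = 25%. The protocol gives no age distribution by band.

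**4. Cross-check on the weights.** 1.63% × 918,000 ≈ 14,970 enrolled, against 11,940 stated. Rounding of the 1.3% gives about 14,400 to 15,600. The band rates therefore probably refer to a narrower base or another date. This supports the denominator point only, and it also means that the width weights are approximate.

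**5. Un-enrolled people per enrolled patient, (1 − p) / p.**

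| Band | p | People per enrolled patient | Observations with 12 index dates (maximum) |
|---|---|---|---|
| Top 0.5% | 0.50 | 1.0 | 12 |
| 0.5-5% | 0.24 | 3.2 | 38 |
| 5-20% | 0.02 | 49 | 588 |

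These ratios precede any restriction to cluster, the requirement to stay un-enrolled to the end of follow-up, and the balancing of covariates.

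**6. Timing.** If the 50% is cumulative to the 11,940 and the top band has the same proportion of 2014 enrolees as the whole programme (assumptions), the top-band ratio per study patient is about 11,940 / 6,360 = 1.9. Further enrolment before the end of follow-up would lower it.

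**7. What a pooled balance rule could miss.** By the width weights, the bands supply 0.25 / 1.63 = 15.3%, 1.08 / 1.63 = 66.3% and 0.30 / 1.63 = 18.4% of enrolled patients. If the other two bands are perfectly balanced and standard deviations are equal (assumptions), the pooled standardised difference is 0.153 times that of the top band. The pooled value stays under 10% until the top band reaches 0.10 / 0.153 ≈ 65%. If the top band's share were double (30.7%), the limit would be 0.10 / 0.307 ≈ 33%.

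**The case against.** The strongest reply is that the plan does not need two distinct people per patient. It selects observations, allows reuse, gives each control up to 12 index dates and falls back to one control. A reader might infer from the 50% rate that the highest-risk patients cannot be matched as planned. The documents do not support that: even one un-enrolled person per enrolled patient yields up to 12 reusable candidate observations. What remains is that index dates and replacement multiply observations, not people.

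A reader might also infer that the two sets of rates cannot describe any single population. That is not shown either. No denominator is stated, a top-5% base removes the conflict, and an unusual age mix could do so. The provable defect is an unstated or mixed denominator.

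It is also tempting to project the top band into a 38% cluster. Assuming a top-5% base, proportional scaling gives 0.50 × 0.38 / 0.266 ≈ 71% enrolled, and scaling on the odds about 63%. That leaves 0.4 to 0.6 people per enrolled patient. This stacks assumptions about denominator, scaling and cumulative enrolment, and should not be relied on.

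Three further points are fair.

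- Within-cluster selection is not a binding rule: controls may come from anywhere in the WELC area, and cluster is not among the listed matching variables.
- The Introduction makes feasibility the first step and names the risk of inadequate matches. Regression adjustment, subgroup credibility criteria and sensitivity analyses follow. None of this corrects the specific assurance given for the top band.
- Balance tables by band could sit in an analysis plan that is not shown. Still, the protocol sets its acceptance rule for the two groups while planning effects by band.

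**Conclusion.** The concern holds in a limited form. The rates quoted do not establish a sufficient control pool within cluster and risk band. On a common top-20% denominator they are incompatible (8.15% against 17% to 38%), so the denominators are mixed or differ from the study population. In the top 0.5% band they leave about one un-enrolled person per enrolled patient: more if the 50% is cumulative and only 2014 enrolees are matched, fewer if enrolment keeps rising. For the 5-20% band the ratio of 49 does suggest an ample pool, subject to cell counts.

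The consequence is heavy reuse of few people and a risk of poor balance in the top band, not a failure to match. The group-level 10% rule may not detect that imbalance. The 65% limit depends on width-based shares, perfect balance elsewhere and equal standard deviations, so it shows what the rule could let through and does not predict what will occur.

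**What to change.** 1. Limit the sufficiency statement to the bands that the figures support. Base it on counts of enrolled and distinct eligible un-enrolled people in each cluster-by-band cell, on the study denominator (age 50 or over, top 20%, CCGs in the data), with the date of the counts.
2. Match exactly on risk band. Where a cell is thin, widen from cluster to CCG.
3. Apply the 10% threshold within each risk band as well as overall. Where a band fails, flag its subgroup estimate as unreliable and show the pooled estimate with and without that band.

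The cost is a wording change, one tabulation and extra balance tables. The downside is looser geographic matching in thin cells and possibly a caveated estimate for one band.
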